## 1. Background and Rationale

### 1.1. Bipolar depression

Bipolar disorder is a mental disorder characterised by episodes of elevated or irritable mood (manic or hypomanic episodes) and episodes of low mood, loss of energy and sadness (depressive episodes). Much of the personal and economic burden of the illness is caused by depressive symptoms (Judd, 2002; Judd, 2003) but there is little randomised evidence to inform treatment. Furthermore, bipolar disorder is associated with increased mortality attributable largely to suicide which most commonly occurs during depressive episodes.

### 1.2. The need for more effective, safer treatments for bipolar depression

In contemporary clinical practice, bipolar depression is often treated with the same medicines as major depressive disorder (also called unipolar depression). In unipolar depression there is strong evidence that antidepressants alleviate symptoms in the short-term and that continued therapy decreases the risk of relapse. In bipolar disorder, by contrast, treatment with antidepressant drugs is complicated by the risk of switching to manic states, the potential for further mood destabilisation and even some doubt about short-term efficacy. These concerns are reflected in the National Institute of Health and Clinical Excellence guidelines on treatment of bipolar depression (NICE, 2006) which recommend that treatment with selective serotonin reuptake inhibitors (SSRIs) should only be used with an antimanic agent and should be discontinued when a patient is in remission from depressive symptoms or symptoms have been significantly less severe for 8 weeks. Furthermore, the guideline recommends that SSRIs should be avoided for patients who have rapid cycling disorder, a recent hypomanic episode or recent functionally impairing, rapid mood fluctuations – which includes a substantial proportion of patients with bipolar disorder. These recommendations indicate considerable uncertainty surrounding treatment of bipolar depression both in the short- and medium-term and the trend away from using antidepressant medicines. At the same time there is an urgent need to identify effective treatments for bipolar depression which:

- provide safe, tolerable and rapid reduction of depressive symptoms
- avoid induction of manic symptoms in the short-term
- maintain continued remission from depressive symptoms and freedom from manic symptoms.

[figure not shown]
### 1.3. Other available treatment for bipolar depression

**1.3.1. Quetiapine:** One of the first-line treatments recommended in the NICE guidelines for acute episodes of bipolar depression is quetiapine (Seroquel®, Astra-Zeneca), an atypical antipsychotic agent. In October 2006 the US Food and Drug Administration (FDA) licensed quetiapine (at a dose of 300mg/day) for treatment of bipolar depression and the European Medicines Evaluation Agency (EMA) granted a license in November 2010.

There are two short-term RCTs of quetiapine in bipolar depression: BOLDER 1 and 2 which had essentially identical designs (Calabrese, 2005; Thase, 2006). In these RCTs, approximately 52% of participants allocated to quetiapine (300mg/day or 600mg/day) had achieved remission by 8 weeks compared to approximately 32% of those allocated to placebo (combined N=978, pooled relative risk [RR] 1.60, 95% CI 1.33 to 1.93 – see Figure 1). There was no evidence that quetiapine increased the risk of manic switching (the rates of hypo(manica) were 2.2% for participants on quetiapine 600 mg/day, 3.9% for those on quetiapine 300 mg/day and 3.9% for those on placebo). A number of adverse events were more frequent on quetiapine than placebo including dry mouth (~40%), sedation (~30%), somnolence (~20%) and dizziness (~20%). The rate of discontinuation of allocated treatment ranged from

[figure not shown]
33% of participants to 46% participants with most withdrawals in the first week post-randomisation. Overall, the trials suggest that quetiapine provides rapid relief of acute depression but with a high incidence of sedation and study withdrawal indicating the need for alternative treatments, especially in the medium-and long-term.

Figure 1: Quetiapine versus placebo – remission by 8 weeks (defined as MADRS  $\leq$  12)

**1.3.2. Lamotrigine:** Lamotrigine (*Lamictal*®, Glaxo-Smith-Kline) is an anticonvulsant which is licensed in the USA and many European countries for the long-term treatment of bipolar disorder and is also often used in the treatment of bipolar depressive episodes. It is well tolerated in the long-term by the majority of patients but can cause skin rashes in up to 10% of patients and, rarely, severe skin reactions including Stevens-Johnson syndrome and toxic epidermal necrolysis. The risk of skin reactions can be reduced by slow dose escalation but this also delays achieving a therapeutic dose and, hence, therapeutic response. A systematic review found five GSK-sponsored trials comparing lamotrigine with placebo in acute phase bipolar depression – only one has been fully published (Geddes, 2006). In an individual patient-level data meta-analysis, patients treated with lamotrigine were more likely to remit (pooled RR 1.21 95% CI 1.03 to 1.42, Heterogeneity chi-squared=5.86 (df=4) p=0.210, Test of RR=1: z=2.30 p=0.021) than those treated with placebo. No adverse events occurred on lamotrigine more frequently than placebo. A recent independent Dutch trial, LAMLIT, found that lamotrigine add-on therapy to lithium was more effective than lithium plus placebo (RR for response 1.61 95% CI 1.05 to 2.53) (van der Loos, 2006). The failure of the individual GSK-sponsored trials to show a drug-placebo difference may reflect under powering due to an overestimation of the likely treatment effect, baseline inflation of depression scores to meet eligibility criteria or be a consequence of the need to build up the dose slowly for safety reasons. Whatever the reason, it has prevented registration of the drug for acute bipolar depression. However, the pooled analysis shows a significant, if modest, treatment effect indicating the potential of lamotrigine for treatment of bipolar depression is worth exploring (see Figure 2).

Figure 2: Lamotrigine versus placebo – remission by 8 weeks (defined as MADRS < 12)

**1.3.3. Quetiapine/lamotrigine combination:** These apparent costs and benefits of quetiapine and lamotrigine raise the possibility that, in combination, they could provide both rapid relief of acute symptoms and longer-term mood stability because:

- in the acute phase the use of quetiapine to reduce depressive symptoms might make the slow introduction of lamotrigine more acceptable
- as the dose of lamotrigine increases, the efficacy of the combination is likely to exceed that of quetiapine alone
- if quetiapine is not tolerated in the longer-term, it can be withdrawn to leave lamotrigine monotherapy at a therapeutic dose.

It is also possible that increased adherence will lead to a functional synergy with combination therapy i.e. greater efficacy than the combined additive benefits of quetiapine and lamotrigine.

**1.3.4. Adjunctive therapy with folic acid:** Folic acid and folate are forms of the water-soluble vitamin B9. Low plasma and red cell folate are thought to be associated with clinical depressive disorders and treatment with folic acid has been shown to improve the therapeutic effect of fluoxetine in depressed patients (Coppin, 2000). Furthermore, case control studies have shown a high incidence of serum and red blood cell folate deficiency in psychiatric patients and lower folate levels have been linked to a poorer response to antidepressant treatment (Fava, 1997). It is possible therefore that addition of folic acid to other treatments for depression may lead to more rapid reduction in depressive symptoms and a lower risk of relapse.

**1.3.5. Genetic studies:** Folic acid is required for DNA synthesis and metabolism of amino acids including homocysteine. A growing number of epidemiological studies suggest links between low folate status, increased homocysteine and depressive symptomatology in the general population (Tiemeier, 2002; Bjelland, 2003; Morris, 2003). There are genetic variations in at least three genes which affect the extent to which folic acid lowers homocysteine levels, or the absorption of dietary folate, and these would therefore be predicted to affect the antidepressant effect of adjunctive folic acid:

- i) 5,10-Methylenetetrahydrofolate reductase (MTHFR) is involved in the conversion of 5,10-methylenetetrahydrofolate to 5-methyltetrahydrofolate which is the main circulating form of folate. The MTHFR C677T single nucleotide polymorphism (SNP) has three genotypes arising from a C/T transition i.e. CC, CT and TT. 677TT homozygotes have only have 30% of enzyme activity and consequently have lower levels of folate (and higher levels of homocysteine) than non-677TT-homozygotes (Refsum, 2006a).
- ii) There is also some evidence for a potential interaction between the catechol-o-methyltransferase (COMT) enzyme genotype and response to treatment with folic acid. The COMT gene has a functional SNP (Val158Met) which alters enzyme activity and Val158 homozygotes have been found to have significantly higher levels of homocysteine than Met158 carriers, The COMT effect was independent of, and additive with, the MTHFR 677TT effect (Tunbridge et al. in press).
- iii) Folate hydrolase 1 (FOLH1) facilitates the transfer of dietary folate into the body. Its activity is modulated by a functional variant in its sequence (T484C): the 484T variant has higher activity than the 484C form. Accordingly, the effects of folate supplementation on homocysteine levels and depressive symptoms may be more pronounced in 484TT homozygotes, compared with 484C carriers (Roffman et al 2013).

CEQUEL will investigate the hypothesis that there will be an interaction between folic acid treatment and genotype at these loci. We predict a greater reduction in homocysteine levels – and also depressive symptoms - in 677TT and Val158 homozygotes. In addition, we hypothesise that the impact of folate on biochemical measures (and depressive symptoms) will be more pronounced in FOLH1 484TT homozygotes.

**1.3.6. B12 status:** There is growing evidence of interactions between vitamin B12 status and folate status, with adverse effects of high folate in those with low B12 status. We will also look at baseline B12 status in relation to outcome measures by analysis of total cobalamin and holotranscobalamin [Refsum, 2006b].

#### **1.4. Summary**

[figure not shown]
There is uncertainty about optimum short- and medium-term treatment for bipolar depression. The combination of lamotrigine plus quetiapine potentially offers enhanced treatment for patients by maximising the benefits of both drugs without inducing mood instability. In addition to this, folic acid is a promising adjunctive therapy for depression. The greater biological homogeneity of bipolar depression would actually make a separate trial of folic acid therapy in bipolar depression worthwhile: however, the proposed trial provides an excellent opportunity to conduct a 2 x 2 factorial design efficiently investigating both the beneficial effects of adding lamotrigine to quetiapine *and* the effects of adding folic acid. The availability of a relevant and measurable function-related metabolite (homocysteine) and good

candidate genes for effect modification will make possible a powerful investigation of the neurobiology of the regulation of mood by folic acid.

## 2. Research Questions

CEQUEL will investigate the effects of adding lamotrigine to quetiapine and the effects of adding folic acid to treatments for bipolar depression. It employs a 2 x 2 factorial (see Figure 3).

Figure 3: Randomisation to lamotrigine vs placebo and to folic acid vs placebo

### 2.1. Principal research questions

1. Does combination therapy with quetiapine plus lamotrigine (Groups 1 & 2) lead to greater improvement in depressive symptoms over 12 weeks than quetiapine monotherapy plus lamotrigine placebo (Groups 3 & 4) in patients with bipolar depressive disorder?
2. Does adjunctive treatment with folic acid (Groups 1 & 3) lead to greater reduction in depressive symptoms by 12 weeks than folic acid placebo (Groups 2 & 4) in patients with bipolar depressive disorder?

### 2.2. Secondary research questions

1. Does combination therapy with quetiapine plus lamotrigine produce superior outcomes to quetiapine monotherapy plus lamotrigine placebo at 12 months?
2. Does adjunctive folic acid produce superior outcomes to folic acid placebo at 12 months?
3. Are there important differences in the relative efficacy, safety and tolerability of quetiapine plus lamotrigine versus quetiapine monotherapy plus lamotrigine placebo between patients with bipolar I disorder and patients with bipolar II disorder and between patients with different levels of baseline severity of depression?
4. Are there important differences in the relative efficacy, safety and tolerability of folic acid and placebo between subgroups of patients defined by genotype (MTHFR C677T, COMT Val158Met and FOLH1 T484C)?
5. Does the baseline homocysteine, folate or vitamin B12 status influence response to folic acid?
6. What are the incremental cost, effects and cost-effectiveness of quetiapine plus lamotrigine combination therapy versus quetiapine monotherapy?
7. What are the incremental costs, effects and cost-effectiveness of folic acid versus placebo?

### 3. Trial Design

CEQUEL is a multicentre, double-blind, randomised, placebo-controlled, parallel group, 2 x 2 factorial clinical trial (see Figure 3) which will include economic, biochemical and genetic analyses. The trial is investigating short-term remission from depressive symptoms and longer-term maintenance of remission and prevention of depressive or manic relapse.

#### 3.1. Outcome measures

**3.1.1. Primary outcome measure:** The primary outcome measure is improvement in depressive symptoms at 12 weeks from the date of randomisation using the Quick Inventory of Depressive Symptomatology, self-report version [QIDS-SR16].

**3.1.2. Secondary outcome measures:**

1. The proportion of participants who both achieve remission by 12 weeks following randomisation (defined as a score of  $\leq 5$  on QIDS-SR16) and remain free from symptomatic relapse by 52 weeks. Depressive relapse is defined as a QIDS-SR16 score  $\geq 10$  on two consecutive weekly ratings and manic relapse as an Altman Self-Rating Mania Scale (ASRM) score of  $\geq 10$  on a single weekly rating.
2. Proportion of time over 12 months when participants were free from manic symptoms (ASRM  $\leq 5$ ).
3. Proportion of time over 12 months when participants were free from depressive symptoms (QIDS-SR16  $\leq 5$ ).
4. New intervention (admission or drug treatment) for manic episode by 52 weeks.
5. New intervention (admission or drug treatment) for depressive episode by 52 weeks.
6. Death (all cause and cause-specific including suicide).
7. Deliberate self-harm.
8. Quality of life – rated using the EuroQol EQ-5D.
9. Unexpected adverse events.
10. Withdrawal from quetiapine or lamotrigine due to adverse effects.
11. Use of health and social care service resources.
12. Social costs/benefits.

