## **8.2. Serious Adverse Event Reporting Procedures**

**8.2.1. Reporting by investigator:** All SAEs, except those SARs that do not require immediate reporting (see 8.2.3.), must be reported to the Chief Investigator (CI) within one working day of discovery or notification of the event. All SAE information must be recorded on an SAE form and emailed/faxed to the CI. Additional information received for an event (follow-up or corrections to the original event data) need to be detailed on a new SAE form and sent/faxed to the sponsor.

In addition to SAE reporting, investigators should report to the CI any non-serious adverse reactions that they consider to be unexpected or for which they consider the severity or duration to be greater than that indicated in the Summary of Product Characteristics (SmPC). Adverse events that lead to withdrawal from the run-in phase or termination of any of the trial treatments during the randomised phase should also be reported.

Investigators are not required to report other non-serious adverse events.

**8.2.2. Reporting by the Chief Investigator:** The CI will:

- report all SUSARs to the Competent Authorities (MHRA in the UK) and the REC concerned. Fatal or life-threatening SUSARs must be reported within 7 days and all other SUSARs within 15 days
- report all SAEs (including SUSARs) to the participant's NHS Trust and to the IDMEC
- inform all investigators concerned of relevant information about SUSARs that could adversely affect the safety of participants.

In addition to the expedited reporting above, the CI will:

- submit once a year throughout the clinical trial or on request a safety report to the Competent Authority (MHRA in the UK), the main REC and participating NHS Trusts and send a copy to the University of Oxford Clinical Trials Research Governance Team.
- provide data on all reported AEs to the IDMEC as required.

**8.2.3. Expected Serious Adverse Reactions:** Immediate reporting of Suspected Serious Adverse Reactions that are listed in the SmPC for the appropriate trial treatment(s) will not be required provided that the severity and seriousness are consistent with the information given in the SmPC.

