**8.3. Reporting Procedures for all Adverse Events**

All SAEs whether observed by the investigator or reported by the participant and whether attributed to trial medication or not, will be reported in the CRF. SAEs considered by the investigator or the CI to be related to the trial medication will be followed until resolution or until the event is considered stable. The following attributes must be assigned by the investigator: description, date of onset and resolution date, severity, assessment of relatedness to trial medication, other suspect drug or device and action taken. The investigator may be asked to provide follow-up information.

It will be left to the investigator's clinical judgment whether or not an SAE is of sufficient severity to require the participant's removal from treatment. A participant may also voluntarily withdraw from treatment due to what he or she perceives as an intolerable AE.

All SAEs that are related to trial medicines or trial procedures and either result in a participant's withdrawal from the trial or are present at the end of the trial should be followed up until symptoms cease or the condition becomes stable.

All deaths occurring on trial must be reported to the CI. These include deaths within 30 days of the final dose of trial medication and deaths up to the last formal follow-up observational period, whichever is longer. For all deaths, available autopsy reports and relevant medical reports will be requested for reporting to the relevant authorities.

Any pregnancy occurring during the trial and the outcome of the pregnancy should be reported to the Chief Investigator.

---

 The severity of events will be assessed on the following scale:  
1 = mild, 2 = moderate, 3 = severe.

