**Appendix 2: Classification of adverse events**

A. Assessment of whether an adverse event is SERIOUS		
	YES	NO
1. Has the participant died?		
2. Was the participant at risk of death because of the AE?		
3. Did the AE lead to admission or extension of admission to hospital?		
4. Has the AE resulted in persistent or significant disability/incapacity?		
5. Was the AE an important medical event that may jeopardise the participant (or an unborn child) and may require medical or surgical intervention to prevent one of the outcomes listed above?		
⇒ If YES to ANY of the questions above, the event is SERIOUS ⇒		

B. Assessment of whether an event is a SUSPECTED ADVERSE REACTION		
	YES	NO
Is a causal relationship between a trial medicine and the adverse event at least a possibility? i.e. a relationship cannot be ruled out.		
⇒ If YES, the event should be classed as a SUSPECTED ADVERSE REACTION ⇒		

C. Assessment of EXPECTEDNESS (Suspected Serious Adverse Reactions only)		
	YES	NO
Is the nature of the adverse reaction consistent with the Summary of Product Characteristics or other relevant product information?		
⇒ If NO, the event should be classed as an UNEXPECTED REACTION ⇒

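### Outcome 9 counts only unexpected adverse events, so known lamotrigine reactions reach a listed outcome only through withdrawal, death or an unexpected feature

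*Protocol*

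**What the plan says.** The secondary outcomes in Protocol section 3.1.2 that bear on harm are:

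- outcomes 4 and 5, new intervention (including admission) for a manic or a depressive episode;
- outcome 6, death, and outcome 7, deliberate self-harm;
- outcome 9, "Unexpected adverse events";
- outcome 10, "Withdrawal from quetiapine or lamotrigine due to adverse effects".

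Outcome 9 has no definition of its own. Elsewhere, expectedness is judged against product information. Section 8.1.5 defines an unexpected serious reaction as one whose nature or severity does not fit that information. Appendix 2, part C, asks: "Is the nature of the adverse reaction consistent with the Summary of Product Characteristics or other relevant product information"?

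Section 1.3.2 says that lamotrigine "can cause skin rashes in up to 10% of patients and, rarely, severe skin reactions including Stevens-Johnson syndrome and toxic epidermal necrolysis".

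On collection, section 8.3 states: "All SAEs whether observed by the investigator or reported by the participant and whether attributed to trial medication or not, will be reported in the" case report form (CRF). Section 8.2.1 adds non-serious reactions that are unexpected, or more severe or longer than the SmPC indicates, and adverse events that end a trial treatment. It then says: "Investigators are not required to report other non-serious adverse events".

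On aims, section 3.2 lists safety and tolerability among the medium- and longer-term outcomes to be investigated. Section 2.2, question 3, begins: "Are there important differences in the relative efficacy, safety and tolerability of quetiapine plus lamotrigine versus quetiapine monotherapy plus lamotrigine placebo", and goes on to ask this between bipolar I and bipolar II patients and between levels of baseline severity. Question 4 asks the same of folic acid between genotype subgroups.

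**The concern.** Expectedness decides how quickly, and to whom, a reaction is reported. It is not a measure of harm. Used as a comparative outcome, it removes the reactions already known for the drug under test, and those are the reactions that a comparison of quetiapine plus lamotrigine with quetiapine plus placebo should estimate.

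A serious skin reaction that is listed in the product information, and does not end treatment, is recorded in the CRF yet belongs to no listed outcome. A report that kept to the outcome list could then describe the safety of the combination without its known serious reactions. The subgroup safety questions in section 2.2 depend on the same measure, because a difference between subgroups cannot be judged without a sound comparison between arms.

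**Working it through.** No figure in the protocol is in dispute. The check follows a known lamotrigine reaction through sections 3.1.2, 8.2.1 and 8.3. It assumes that the reactions named in section 1.3.2 are listed in the product information, which is not among the documents.

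| Known skin reaction | Recorded? | Enters a listed outcome? |
|---|---|---|
| Fatal | Yes (8.3) | Yes, outcome 6 |
| Ends lamotrigine or quetiapine, serious or not | Yes (8.2.1, 8.3) | Yes, outcome 10 |
| Nature or severity does not fit the SmPC | Yes (8.2.1, 8.3) | Yes, outcome 9, if judged unexpected |
| Serious, expected, treatment continues | Yes, CRF (8.3) | No |
| Non-serious, expected, treatment continues, no worse or longer than the SmPC indicates | Not required (8.2.1) | No |

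The fourth row is lost through the wording of the outcome, although the data exist. The fifth row is lost through the collection rule, so no later analysis can restore it.

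Outcome 10 is only a partial substitute. It depends on treatment being stopped. As worded, it pools quetiapine, which every participant takes, with lamotrigine. It does not count withdrawal from folic acid, so for the folic acid comparison outcome 9 is the only general adverse-event measure that covers the folic acid itself.

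Scale:

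- Section 9.2 plans 236 participants with equal allocation: 236 / 2 = 118 per lamotrigine margin.
- At the upper rate of 10% in section 1.3.2: 118 × 0.10 = 11.8 rashes. At an assumed 5%: 118 × 0.05 = 5.9.
- Rashes that end treatment, or that are reportable for severity or duration, must be subtracted. The protocol gives no share for either, so the number in the fifth row cannot be computed. About 12 is an upper bound.

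Would recording rash be informative? With n = 118 per group, two-sided 5% and the normal approximation, power = Φ[(d − 1.96·s0)/s1]. Here d = p1 − p0, s0 = √(2·p̄(1 − p̄)/n), s1 = √((p1(1 − p1) + p0(1 − p0))/n), and p̄ is the mean of p1 and p0. With p1 = 0.10 and assumed placebo rates:

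| Placebo rate p0 (assumed) | Power |
|---|---|
| 0% | 95% |
| 2% | 74% |
| 5% | 31% |

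So a rash comparison could be informative, depending on a placebo rate that the protocol does not give.

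**The case against.** The strongest reply is that harms are covered from several sides. Outcome 10 has no expectedness filter, and outcomes 4 to 7 cover mood admissions, death and self-harm. All SAEs are in the CRF, and under section 8.2.2 data on all reported adverse events go to the IDMEC as required. An SAP, not shown here, could tabulate SAEs by arm. Selective reporting of non-serious events is openly stated and suits a trial built into routine care. Section 1.3.2 also reports that, in the pooled lamotrigine trials, no adverse event was more frequent than on placebo.

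Much of this stands, and it rules out several stronger readings that a reader might infer:

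- *Outcome 9 is the only adverse-event outcome, so known harms escape comparison altogether.* They do not: outcomes 6 and 10 count those that are fatal or end treatment.
- *The outcome selects for events unrelated to the drug and biases the comparison toward no difference.* Outcome 9 leaves its term undefined. In sections 8.1.5 and 8.2.1 and in Appendix 2, unexpectedness qualifies suspected drug reactions. The protocol does not show that unrelated events count, and no such claim is made here.
- *Twelve rashes would be lost.* That is a ceiling, with no placebo rate and no deduction for rashes captured elsewhere.
- *Question 3 asks for the overall safety comparison.* It is a subgroup question. The general aim is in section 3.2.

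What the reply does not remove is that the protocol itself fixes an outcome with this filter. An SAP may add tables, but the stated outcome, followed as written, leaves out expected serious reactions that do not end treatment. Nor can an SAP recover events that were never collected.

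**Conclusion.** The point holds. Outcome 9 uses a regulatory reporting filter as a comparative safety outcome, and no listed outcome compares all SAEs or all reported adverse events between arms. Known lamotrigine reactions enter the outcome list only through withdrawal, death or an unexpected feature, which is narrower than the safety and tolerability aim in section 3.2.

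The number of events affected is not computable from the protocol. For serious skin reactions no rate is given beyond their being rare. For rash, about 12 per lamotrigine margin is the upper bound. The conclusion assumes that the named reactions are in the product information and that outcome 9 uses expectedness as the rest of the protocol does. The primary outcome and the sample size are not touched. The outcome should be reworded because the defect is in the stated definition and costs almost nothing to correct.

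**What to change.** Restate outcome 9 in section 3.1.2 as: *all serious adverse events, expected or unexpected, overall and by type, and all adverse events reportable under section 8.2.1*, compared by allocated treatment at each margin (lamotrigine against placebo, folic acid against placebo). The events are already collected under sections 8.2.1 and 8.3, so the cost is a wording change and the matching tables.

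Optionally, add a rash yes/no item at the 12- and 52-week visits (sections 5.3.1 and 5.5.1). This would record the expected, non-serious rashes that section 8.2.1 leaves unreported, at a small burden to sites. The 22-week form is less suitable, because section 5.4 allows it to be completed without the participant present. Neither change alters treatment or its management.
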